To determine whether the addition of sorafenib to TACE (performed according to a standardised protocol with doxorubicin eluting beads) is superior to TACE alone in the treatment of HCC

Sample Size

The trial aims to recruit 206 patients in each arm (412 patients in total)

Trial Duration

It is anticipated that recruitment will take approximately three years and the study will continue for a further year after the last patient has been recruited. Estimated start date for recruitment is November 2010 and will end by first quarter 2015. All patients will be followed up for one year after the last administration of sorafenib/placebo and will be flagged with the Medical Research Information Service until death.

Outcome Measures

Primary: Progression Free Survival

Secondary: Overall Survival; Time to Progression; Toxicity; Disease Control (CR+PR+SD); QoL and number of TACE procedures performed during 12 months following randomisation

Eligibility Criteria

Inclusion Criteria

[figure not shown]
- Histological or cytological diagnosis or meet the AASLD criteria (Appendix 1) for diagnosis of HCC and at least one uni-dimensional lesion measurable according to the RECIST criteria by CT-scan or MRI (Appendix 2)
- Not a candidate for surgical resection or liver transplant
- Aged ≥18 years and estimated life expectancy >3 months
- ECOG performance status ≤1 (Appendix 3)
- Adequate haematological function Hb ≥9g/L, absolute neutrophil count ≥1.5x10⁹/L, platelet count ≥60x10⁹/L
- Bilirubin ≤50 µmol/L, AST or ALT ≤5 x ULN, ALP <4 x ULN
- Adequate renal function; Creatinine ≤1.5 x ULN
- INR ≤1.5
- Amylase <2 x ULN
- Child-Pugh cirrhosis A (score must be ≤6) (Appendix 4)
- Left Ventricular Ejection fraction ≥45%
- Women of child-bearing potential should have a negative pregnancy test prior to study entry. Both men and women must be using an adequate contraception method, which must be continued for 3 months after completion of treatment
- Written informed consent

Exclusion Criteria

- Extrahepatic metastasis
- Prior embolisation, systemic or radiation therapy for HCC
- Any contraindications for hepatic embolisation procedures including portosystemic shunt, hepatofugal blood flow, known severe atheromatosis
- Investigational therapy or major surgery within 4 weeks of trial entry
- Any ablative therapy (RFA or PEI) for HCC (this should not exclude patients if target lesion(s) have not been treated and occurred >6 weeks prior to study entry)

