2 AIMS, OBJECTIVES AND OUTCOME MEASURES

• The primary objective

The primary objective is to determine whether the addition of sorafenib to TACE, performed with doxorubicin eluting beads (DC Bead[®], Biocompatibles), prolongs progression free survival in patients with HCC compared to TACE alone.

• The secondary objectives

The secondary objectives are to determine whether the addition of sorafenib to TACE performed with doxorubicin eluting beads (DC Bead[®], Biocompatibles):-

- prolongs overall survival
- prolongs time to progression
- has acceptable toxicity
- affects disease response (CR & PR & SD)
- affects Quality of Life (QoL)
- reduces the frequency for repeat TACE as measured by number of TACE procedures performed in 12 months following randomisation

Translational sub-studies

A blood sample bank linked to this study will be established for biomarker research (proteomic and genomic analysis). Patients will be invited to provide additional blood samples for research. A TACE-2 Translational Study Patient Information Sheet will be provided and patients will indicate their consent on the TACE-2 Translational Study consent from. Refusal to consent to this additional blood collection will not exclude the patient's participation in the therapeutic trial. Blood will be collected at screening,

randomisation, within 24 hours before 1st TACE, 24 hours after 1st TACE and at week 10 and 22 post randomisation. A standard operating procedure will be provided. Patients will also be invited to provide consent for research to be performed on residual tumour or liver tissue that has been taken for diagnostic purposes. Separate protocols will be written for each sub-study that will use the samples provided and ethical approval will be sought from the appropriate ethics committee. Following the closure of the trial no further blood samples will be sought from patients. Any existing samples retained at sites shall be sent to the blood sample bank.

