12.5 Disease Control [CR+PR+SD] and progression [PD]

Response will be assessed using the RECIST guidelines. Response according to modified RECIST criteria will also be recorded separately but only PD by RECIST will trigger unblinding. The scan done prior to randomisation will be considered the baseline scan and the same modality must be used for all follow-up assessments. PD will be externally validated. Unblinding will occur upon local diagnosis of PD confirmed by receipt at the Trials Unit of a Progression Notification Form, signed by the PI. (See also section 3.2)

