Objective Disease Response will be determined according to the RECIST criteria and patients will be grouped for comparison across treatments according to their 'best' response. Response rates are calculated by dividing the total number of patients with CR or PR (on 'best' response) by the total number of patients randomised per treatment group. The proportions of patients achieving a response will be compared descriptively with 95% CI and compared across treatments using Pearson's chi-square test.

Quality of life will be analysed using longitudinal statistical methods comparing treatment group with appropriate consideration given to missing data due to dropout and death. Questionnaire responses will be combined and transformed into dimension scores and the mean change from baseline score compared using the Mann-Whitney test. Standardised area under the curve analysis will be used to assess mean observed symptomatic and functional QoL over a complete period of 12 months from randomisation whilst minimising multiple testing. Global QoL scores and utility scores form the EQ-5D will be assessed in a quality-adjusted survival analysis to enable simultaneous assessment of QoL and survival, to account for drop-out due to death and censored QoL estimates (from patients remaining alive). Quality adjusted survival analysis within 12 months of randomisation using the integrated quality-survival product method will be used.

The number of additional TACE procedures will be recorded in each arm and reported descriptively with medians and ranges.

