2.2.1 Frequency of tumour re-evaluations

For the TACE-2 trial, Progression Free Survival (PFS) and disease control (CR+PR+SD) will be evaluated clinically and radiologically by a CT scan of the abdomen and chest at baseline, week 10, week 22 and then at 3 monthly intervals until progression or end of study or death.

3 Reporting Of Results

All patients included in the study must be assessed for response to treatment, even if there are major protocol treatment deviations or if they are ineligible. Each patient will be assigned one of the following categories: 1) complete response, 2) partial response, 3) stable disease, 4) progressive disease, 5) early death from malignant disease, 6) early death from toxicity, 7) early death because of other cause, or 9) unknown (not assessable, insufficient data). (Note: By arbitrary convention, category 9 usually designates the "unknown" status of any type of data in a clinical database)

All of the patients who met the eligibility **criteria** should be included in the main analysis of the **response** rate. Patients in **response** categories 4-9 should be considered as failing to respond to treatment (disease progression). Thus, an incorrect treatment schedule or drug administration does not result in exclusion from the analysis of the **response** rate. Precise definitions for categories 4-9 will be protocol specific.

All conclusions should be based on all patients.

Subanalyses may then be performed on the basis of a subset of patients, excluding those for whom major protocol deviations have been identified (e.g. early death due to other reasons, early discontinuation of treatment, major protocol violations, etc). However, these subanalyses may not serve as the basis for drawing conclusions concerning treatment efficacy, and the reasons for excluding patients from the analysis should be clearly reported. The 95% confidence intervals should be provided.

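### The declared secondary outcome is disease control (CR+PR+SD), but section 13.2 specifies a rate, confidence interval and test only for CR or PR

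*Protocol*

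**What the plan says.** Four places in the protocol name the outcome, and all of them include stable disease.

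- Synopsis, Outcome Measures, secondary list: "Disease Control (CR+PR+SD); QoL and number of TACE procedures performed during 12 months following randomisation".
- Section 2, secondary objectives: whether adding sorafenib "affects disease response (CR & PR & SD").
- Section 12.5, heading of the outcome definition: "12.5 Disease Control [CR+PR+SD] and progression [PD"].
- Appendix 2, section 2.2.1: "disease control (CR+PR+SD) will be evaluated clinically and radiologically".

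Section 3.2 lists the outcome only as disease response and gives no definition.

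The analysis is in section 13.2, in a paragraph on objective disease response. It first says that "patients will be grouped for comparison across treatments according to their 'best' response". It then sets the numerator: "Response rates are calculated by dividing the total number of patients with CR or PR" on best response, divided by all patients randomised in the arm. Finally it sets the comparison: "The proportions of patients achieving a response will be compared descriptively with 95% CI and compared across treatments using Pearson's chi-square test". The protocol has no other analysis text for this outcome.

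**The concern.** A patient whose best response is stable disease is a success under the declared outcome and a non-success under the proportion tested in section 13.2. The two sections describe different endpoints.

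This goes beyond a detail that a protocol may leave to its SAP. Section 13.2 is not silent: it fixes a numerator, a denominator, an interval and a test. A SAP that follows it carries the mismatch forward, and a SAP that analyses CR+PR+SD departs from it. While both versions stand, either could be presented as the planned secondary result, and the choice could be made after the data are seen.

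**Working it through.** The question is mainly one of text, so the declared outcome and the analysis are set side by side.

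| | Declared outcome (synopsis, 2, 12.5, Appendix 2) | Analysed proportion (13.2) |
|---|---|---|
| Name | Disease control; disease response in section 2 | Objective disease response |
| CR | success | success |
| PR | success | success |
| SD | success | not a success |
| PD | not a success | not a success |
| Denominator | not stated | all randomised, per arm |
| Rate, CI, test | none stated | rate, 95% CI, Pearson chi-square |

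**Step 1. Is the declared outcome analysed elsewhere?** The rest of section 13.2 covers PFS, overall survival, time to progression, toxicity, quality of life and number of TACE procedures. Sections 13.3 to 13.6 cover subgroups, interim and final analyses, and the exploratory Bayesian analysis. None gives a CR+PR+SD proportion, interval or test.

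**Step 2. Is the analysed proportion a declared outcome?** CR or PR alone is not listed in the synopsis, section 2 or section 12. The undefined term in section 3.2 could be read that way, but section 2 uses nearly the same term and spells it out with stable disease included.

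**Step 3. Can the two proportions differ materially?** The protocol sets no target or expected rate for either, so there is no plan figure to reproduce. Section 1.3 gives one illustration, the sorafenib phase II trial:

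- CR or PR: 2.2%.
- Stable disease: 33.6% (over 16 weeks).
- CR+PR+SD: 2.2% + 33.6% = 35.8%. The sum is approximate because the stable disease figure carries its own duration condition.
- Share of disease control made up of stable disease: 33.6 / 35.8 = 94%.

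Those patients had advanced disease and received no TACE. The figures show that the proportions can diverge, not what either will be in this trial.

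**Step 4. Is anything else touched?** Section 13.1 sizes the trial on PFS alone. With a hazard ratio of 0.72, two-sided 5% significance and 85% power, Freedman's formula gives (1.960 + 1.036)² × (1.72 / 0.28)² = 339 events and Schoenfeld's gives 4 × (1.960 + 1.036)² / (ln 0.72)² = 333, against at least 340 stated. Neither calculation uses a response or disease control rate, so the sizing is independent of this point.

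**The case against.** Four points can be made in the protocol's defence.

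- **Stable disease would be visible.** Section 13.2 groups patients by best response across arms, and the RECIST categories in Appendix 2 include stable disease. A table by arm would let a reader add CR, PR and SD. This stands, and a reader who infers that disease control would never be compared in any form goes too far. What is missing is a stated rate with its interval and test.
- **The SAP may supply the analysis.** Section 13.2 refers to a detailed SAP, which is not at hand. This limits the finding to the protocol text: it cannot be said that the trial will fail to address its secondary objective. It does not remove the conflict, because section 13.2 already fixes a rule for a different endpoint.
- **The naming is loose throughout.** Sections 2 and 3.2 speak of disease response, so the drafters may have used the terms interchangeably. That may explain the conflict, but the category lists still differ. The looseness does argue against one stronger reading, that objective response would be passed off as disease control: section 13.2 labels its analysis as objective response, so nothing is mislabelled.
- **Other endpoints carry the information.** PFS and time to progression are compared by log-rank test and capture the distinction between stable and progressive disease over time. This is true and reduces the consequence, but disease control is still listed as an outcome in its own right.

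**Conclusion.** The point holds for the protocol text. Four places declare CR+PR+SD, while section 13.2 gives a rate, interval and test only for CR or PR. The declared outcome has no stated analysis, and the tested proportion is not a declared outcome. One secondary outcome is affected; the primary PFS analysis and the sample size are not. It should be corrected, but it does not threaten the trial's main conclusion.

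Two further inferences are tempting and not supported.

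- A reader might argue that the CR or PR test is futile because sorafenib barely moved response in the SHARP trial (2.3% against 0.7%, section 1.3). That would mean adding the 1.6-point difference to the 44% to 50% RECIST response quoted for DC Bead in section 1.2. Nothing in the protocol supports that addition, and section 1.4 says that the earlier sorafenib patients would not have been suitable for TACE. Low power for a secondary proportion is in any case no defect in a trial sized on PFS.
- A reader might conclude that disease control has to be assessed at the week 22 scan. No section says so, and section 13.2 works on best response. A week 22 proportion with progression, death and missing scans counted as failures would be a new endpoint, close to PFS at 22 weeks.

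The verdict assumes only that the current protocol wording is what the analysis will follow.

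**What to change.** In section 13.2:

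1. Define the disease control rate as patients with CR, PR or SD by RECIST, on best response as that section already uses, divided by all patients randomised in each arm.
2. Compare it between arms with a 95% CI and the Pearson chi-square test already named there.
3. Keep CR or PR over all randomised as a separate summary, labelled objective response.

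Then use one outcome name and one category list in sections 2, 3.2, 12.5 and 13.2, and make sure that the SAP matches.

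The cost is a wording amendment. The RECIST assessments are already collected, so no extra scans, patients or data are needed.

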11 QUALITY OF LIFE

QoL is an important outcome measure and as such all patients will be invited to participate in the QoL study. Patients who consent will be assessed using validated instruments developed by the EORTC QoL Group: the EORTC QoL questionnaire (QLQ-C30) version 3 and EORTC QLQ-HCC18 a site-specific module for HCC. The EORTC questionnaires will assess both general and hepatocellular specific aspects of quality of life. Patients will also be asked to complete a EuroQoL (EQ-5D) questionnaire which will enable the patient's current health state to be valued for use in calculating quality-adjusted life years (QALYs). These will be collated into a QoL booklet which will be given to patients to complete prior to treatment with the reasons for any non-compliance recorded. QoL booklets will be coordinated with routine clinic visits and requested at baseline, pre TACE, week 10 and 6-weekly thereafter until progression.

The EORTC QLQ-HCC18 site-specific module for HCC has completed phases 1 to 3 of questionnaire development, and has been approved by the EORTC module development committee and currently submitted for publication.

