12.6 Quality of Life (QoL)

QoL will be assessed using the EORTC QoL questionnaire (QLQ-C30) version 3, EORTC QLQ-HCC18, a site-specific module for HCC and the EuroQoL (EQ-5D) questionnaire

requested at baseline, pre TACE, week 10 and 6-weekly thereafter until progression. QoL will be scored according to the EORTC QLQ-C30 manual and guidelines.

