tailed 5% significance level. Recruiting 206 patients in each treatment arm over a 36 month period, with additional follow-up of 12-months following the recruitment period, will allow these survival differences to be detected using a 2-sided level of significance of α =0.05 with 85% power. If the true median survival times are 8.9 and 12.4 months for TACE with placebo and sorafenib respectively, the null hypothesis that the survival distributions are equal can be rejected with 85% power. Numbers of patients are estimated using PS software (version 3.0.2) developed by Dupont and Plummer at Vanderbilt University and which is available free from their website. The software is based on methods described by Schoenfeld and Richter in Biometrics 1982.

Machin and Campbell sample size software (version 2.5) calculate that the study will require at least 340 events to achieve 85% power, as above.

The assumptions behind these sample size calculations will be re-examined periodically by an independent data monitoring committee during the course of the trial, and modified as appropriate.

The number of patients lost to follow-up for the primary outcome measure is expected to be minimal (existing studies report \leq 6%) but will obviously be monitored rigorously. The Data Monitoring Committee (DMC) may advise recruitment of additional patients based on the number of patients lost to follow up if numbers are higher than anticipated. The number of patients who do not comply with the protocol is expected to be low. All protocol violators will be reported but will be included in the final analysis within their randomised group on an intention-to-treat basis.

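### The change-from-baseline comparison of quality-of-life scores names a mean but tests it with Mann-Whitney, which does not target a mean and uses baseline only by subtraction

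*Protocol*

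**What the plan says.** Section 2 lists as a secondary objective whether adding sorafenib to TACE "affects Quality of Life (QoL"). Section 11 has the questionnaires "requested at baseline, pre TACE, week 10 and 6-weekly thereafter until progression", and Section 12.6 adds that "QoL will be scored according to the EORTC QLQ-C30 manual and guidelines".

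The QoL paragraph of Section 13.2 then plans four things:

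- "Quality of life will be analysed using longitudinal statistical methods comparing treatment group", with attention to missing data from dropout and death; no model is named.
- Dimension scores, with "the mean change from baseline score compared using the Mann-Whitney test".
- A standardised area-under-the-curve summary of average symptom and function scores for the first year.
- "Quality adjusted survival analysis within 12 months of randomisation using the integrated quality-survival product method will be used".

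The point concerns the second item only. Details are referred to a statistical analysis plan that was not available for this review, but the pairing of mean change with Mann-Whitney is fixed in the protocol itself.

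**The concern.** Mann-Whitney on change scores responds to the probability that a patient on one arm has a larger change than a patient on the other. That agrees with a difference in means when the treatment shifts everyone's score by about the same amount. It need not agree when some patients are hurt and others are not. The protocol's background gives some reason to expect unevenness: in the large placebo-controlled trial in advanced disease (Section 1.3), 8% had grade 3/4 diarrhoea and hand-foot skin reaction, and 32% needed a dose reduction.

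Two things are at stake. A sentence reporting that mean change differed, or did not, could rest on a test that answers another question. And a baseline score that the protocol already collects is not used as a covariate, which costs precision.

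**Working it through.** **Plan's own figure.** The protocol gives no power figure for QoL. Its only one is for PFS, 340 events for 85% power at hazard ratio 0.72, and it reproduces: (1.960 + 1.036)² × (1.72/0.28)² = 8.978 × 37.73 = 339. It has no bearing here.

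**Inputs.** From Section 13.1: "Recruiting 206 patients in each treatment arm over a 36 month period". QoL participation is by separate consent and stops at progression, so 206 is an upper limit. Assumed, because the protocol gives neither: score SD σ = 20, baseline to follow-up correlation ρ = 0.5, approximately normal scores, two-sided 5%.

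**Building blocks.**

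- SD of change = σ√(2(1−ρ)) = 20.
- ANCOVA residual SD = σ√(1−ρ²) = 17.32.
- θ is the probability that a sorafenib change is worse than a placebo change. Under the null its standard error is √((1/206 + 1/206)/12) = 0.0284.
- Power ≈ Φ(z − 1.96) + Φ(−z − 1.96).

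**Uniform 5-point worsening.**

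- Mann-Whitney: θ = Φ(5/28.28) = 0.570; z = 0.0702/0.0284 = 2.47; power 69%.
- Welch on change: SE = 20√(2/206) = 1.971; z = 2.54; power 72%.
- ANCOVA: SE = 17.32√(2/206) = 1.707; z = 2.93; power 83%.

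Simulation gives 70/72/84%. Of the 14 points, 2 to 3 come from ranking and the rest from not adjusting for baseline. With ρ = 0.4 the Mann-Whitney and ANCOVA powers are 62% and 79%; with ρ = 0.6 they are 79% and 89%. At ρ = 0.5 they are 56% and 71% with 150 per arm, and 41% and 53% with 100.

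**A fraction f worsens by d points.** The mean difference is fd. The sorafenib-arm variance grows by f(1−f)d². θ = (1−f)/2 + fΦ(d/28.28). For f = 15% and d = 50:

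- The mean difference is 7.5 and the added variance is 318.75.
- Mann-Whitney: θ = 0.569, z = 2.43, power 68%.
- Welch: SE = √((400 + 718.75)/206) = 2.330, z = 3.22, power 90%.
- ANCOVA: SE = √((300 + 618.75)/206) = 2.112, z = 3.55, power 94%.

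| Pattern, 206 per arm | Mann-Whitney | Welch | ANCOVA | Mann-Whitney vs ANCOVA |
|---|---|---|---|---|
| 8% lose 30 | 17% | 22% | 27% | 10 points |
| 32% lose 20 | 83% | 87% | 94% | 11 points |
| 15% lose 50 | 68% | 90% | 94% | 26 points |
| 10% lose 60 | 40% | 73% | 81% | 41 points |

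Simulation with scores rounded to a grid and kept within 0-100 gives 39/68/77% for the last row, a gap of 38 points. The other rows move by 2 points or less.

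**Equal means.** A fraction f loses d and the rest gain g = fd/(1−f), so θ = (1−f)Φ(−g/28.28) + fΦ(d/28.28). Mann-Whitney then rejects as follows:

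- 15% lose 50, the rest gain 8.8: θ = 0.465, z = 1.23, rejects 23% (simulation 22-24%).
- 20% lose 40, the rest gain 10: 15%.
- 20% lose 30, the rest gain 7.5: 7%.

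Welch and ANCOVA stay at about 5%. These cases use an unbounded scale. The rate depends heavily on the spread of change: if the harm is offset by shifting the whole arm up, an SD of change of 28 gives about 5-7%. An SD of change of 10 (ρ = 0.875 at σ = 20) gives 64-93%.

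**The case against.** The strongest reply is that this is one sentence among several. The same paragraph promises longitudinal methods, an area-under-the-curve analysis of mean QoL and a quality-adjusted survival analysis. Grade 3/4 toxicity is reported separately, so serious harm in a minority would show there too. Covariates and reporting format belong in the statistical analysis plan. Ranks are a defensible choice for bounded, coarse, skewed scores and can win: with heavy-tailed change scores (t, 3 df) and a uniform 3-point shift, simulation gave Mann-Whitney 78-85% power against 61-65% for Welch or ANCOVA. The large losses above need 10-15% of patients to lose 50-60 points on a 100-point scale. Nearer the protocol's own 8% and 32%, ranks rather than means cost about 3 to 6 points. The equal-means case needs near-exact cancellation, and rejecting there is correct detection of a distributional difference under Mann-Whitney's own null.

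All of that stands as a limit on size. It also rules out stronger readings that a reader might infer:

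- That the test ignores baseline: it does not, because change from baseline subtracts it.
- That mean harm would be missed: power is lower, not absent, and other analyses address mean QoL.
- That no effect on QoL will be estimated: this does not follow, since the other analyses can supply estimates. Only this comparison has none attached.

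The objection does not remove the mismatch. The sentence might instead mean each patient's own average change over visits, ranked between arms; that would still not compare arm means, and the wording does not settle it.

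**Conclusion.** The point holds in limited form. The protocol states a mean change and fixes a test that does not target it, and it leaves out a covariate adjustment that costs nothing to collect. With SD 20, correlation 0.5 and 206 per arm, the loss against ANCOVA is about 9 to 14 points of power for diffuse or mild effects, most of it from the unadjusted baseline in the uniform-shift case. It reaches about 25 to 38 points only under large harm confined to 10-15% of patients. Rejection above 5% with equal means is real but secondary. All of these sizes rest on assumed distributions; the mismatch between quantity and test does not. QoL is a secondary outcome, and neither PFS nor the trial's main conclusion is touched.

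**What to change.** In Section 13.2, replace the mean-change and Mann-Whitney phrase with wording such as: the between-arm difference in mean dimension score, with 95% confidence interval, adjusted for baseline score, from the longitudinal model (ANCOVA where a single visit is analysed), with robust standard errors. State which visits or summary over visits it refers to, which also removes the ambiguity over each patient's own mean. Keep Mann-Whitney as a labelled sensitivity analysis for a distributional shift.

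The cost is a wording change, matching text in the statistical analysis plan and minor programming. No new data, visits or patients are needed, because baseline QoL is already collected. The downsides are small: reliance on large-sample normality of means, and lower power than ranks if change scores turn out heavy-tailed, which the retained rank test would help to show.
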